#### 15.4.2 Serious Adverse Event (SAE)

Information about all serious adverse events will be collected and recorded. A serious adverse event is an undesirable sign, symptom or medical condition which:

- Is fatal or life-threatening
- Results in persistent or significant disability/incapacity
- Is medically significant, i.e., defined as an event that jeopardizes the patient or may require medical or surgical intervention to prevent one of the outcomes listed above
- Causes congenital anomaly or birth defect
- Requires inpatient hospitalization or prolongation of existing hospitalization, unless hospitalization is for:
  - Routine treatment or monitoring of the studied indication, not associated with any deterioration in condition (procedures such as central line placements, paracentesis, pain control)
  - Elective or pre-planned treatment for a pre-existing condition that is unrelated to the indication under study and has not worsened since the start of study drug
  - Treatment on an emergency outpatient basis for an event not fulfilling any of the definitions of a SAE given above and not resulting in hospital admission > 24 hours.
  - Social reasons and respite care in the absence of any deterioration in the patient's general condition

Collection of adverse events will begin after the first dose of study treatment and end 30 days after the last dose of study treatment.

Any death (except those due to progression of disease) from any cause while a patient is receiving treatment on this protocol or up to 30 days after the last dose of protocol treatment, or any death which occurs more than 30 days after protocol treatment has ended but which is felt to be treatment related, must be reported.

Toxicities which fall within the definitions listed above must be reported as an SAE regardless if they are felt to be treatment related or not. Toxicities unrelated to treatment that do NOT fall within the SAE definitions above or AESIs in section 15.5.3 must simply be documented as AEs in the patient research chart.

#### 15.4.3 Adverse Events of Special Interest

AESIs (serious or nonserious) are defined as AEs of scientific and medical concern specific to the Clovis's product or program, for which ongoing monitoring and rapid communication by the investigator to Clovis can be appropriate. Such an event might warrant further investigation in order to characterize and understand it. Depending on the nature of the event, rapid communication by the Sponsor-Investigator to other parties (e.g., regulators) might also be warranted.

Details on Clovis's currently agreed list of AESIs for rucaparib can be found in the current rucaparib IB. These AESIs are to be reported to Clovis expeditiously within 48 hours of knowledge of the event, during the study through 30 days after receiving the last dose of study treatment, according to the procedures below.

### 15.5 SAE Reporting Requirements

SAEs must be reported to the DSMC, the FDA, the IRB, and drug manufacturer according to the requirements described below:

A MedWatch 3500A form must be completed and submitted to [[contact]](mailto:[contact]) as soon as possible, but no later than 1 business day after first knowledge or notification of event.

#### DSMC Notifications:

An HCI Research Compliance Officer (RCO) will process and submit the MedWatch form to the proper DSMC member as necessary for each individual study.

The RCO will summarize and present all reported SAEs according to the Data and Safety Monitoring Plan at the quarterly DSMC meeting.

#### FDA Notifications:

This study is IND exempt; therefore, there are no SAE reporting requirements to the FDA

#### IRB Notification:

Events meeting the University of Utah IRB or local IRB reporting requirements will be submitted per local guidelines.

#### Drug Manufacturer Notifications:

All SAEs and AESIs, regardless of relationship to study drug, must be reported to Clovis Pharmacovigilance within 24 hours of knowledge of the event, during the study through 30 days after receiving the last dose of study treatment, according to the procedures below. After the 30 day specified window, only SAEs considered to be treatment related and all AESIs, regardless of treatment relationship, should be reported. It is important that the investigator provide an assessment of relationship of the SAE or AESI to study treatment at the time of the initial report.

Reporting will be done via email: [[contact]](mailto:[contact]).

## **15.6 Reporting of Pregnancy**

Although pregnancy is not considered an adverse event, it is the responsibility of investigators or their designees to report any pregnancy or lactation in a subject, including the pregnancy of a male subjects' female partner as an SAE. Pregnancies or lactation that occurs during the course of the trial or with 6 months of completing the trial or starting another new anticancer therapy, whichever is earlier, must be reported to the DSMC, IRB, FDA, and the sponsor as applicable. All subjects and female partners who become pregnant must be followed to the completion/termination of the pregnancy. Pregnancy outcomes of spontaneous abortion, missed abortion, fetal death, intrauterine death, miscarriage and stillbirth must be reported as serious events.

## **15.7 Protocol Amendments**

Any amendments or administrative changes to an IRB approved protocol will not be initiated without submission of an amendment for IRB review and approval.

These requirements for approval will in no way prevent any immediate action from being taken by the investigator in the interests of preserving the safety of all patients included in the trial.

Any amendments to the protocol that significantly affect the safety of subjects, scope of the investigation, or the scientific quality of the study are required to submit the amendment for FDA review.

## **15.8 Protocol Deviations**

A protocol deviation (or violation) is any departure from the defined procedures and treatment plans as outlined in the protocol version submitted and previously approved by the IRB. Protocol deviations have the potential to place participants at risk and can also undermine the scientific integrity of the study thus jeopardizing the justification for the research. Protocol deviations are unplanned and unintentional events.

Because some protocol deviations pose no conceivable threat to participant safety or scientific integrity, reporting is left to the discretion of the PI within the context of the guidelines below. The sponsor requires the **prompt reporting** to HCI RCO of protocol deviations which are:

- Exceptions to eligibility criteria.
- Intended to eliminate apparent immediate hazard to a research participant or
- Harmful (caused harm to participants or others, or place them at increased risk of harm - including physical, psychological, economic, or social harm), or
- Possible serious or continued noncompliance

## **15.9 FDA Annual Reporting**

This study is IND exempt therefore there are no annual reporting requirements to the FDA.

## **15.10 Clinical Trials Data Bank**

The study will be registered on <http://clinicaltrials.gov> and the NCI CTRP (Clinical Trials Reporting Program) by the Clinical Trials Office.

## **15.11 Record Keeping**

Per 21 CFR 312.57, Investigator records shall be maintained for a period of 2 years following the date a marketing application is approved; or, if no application is filed or the application is not approved, until 2 years after the investigation is discontinued and the FDA is notified.

## APPENDIX A — Rucaparib Dosing Diary

Page 1/2

**Patient Initials:** \_\_\_\_\_

**Patient Study ID:** \_\_\_\_\_

**Treatment Cycle #:** \_\_\_\_\_

**Dose:** \_\_\_\_\_

- 1) Take the number of pills prescribed by your study doctor twice a day at approximately the same time each day. Take your pills with an 8oz glass of water with or without food.
- 2) If you forget to take your pills at the right time, you can take them as soon as you remember on that day as long as it's not more than 4 hours after the usual time.
- 3) If you miss taking your pills by more than 4 hours, the dose is missed. Do not take extra pills with your next dose to try and make up for the missed dose.
- 4) Complete one line of the diary each day and write the total number of pills taken in the morning and in the evening. If you've missed a dose, briefly explain why in the comments.
- 5) Please bring this diary as well as all empty containers and any unused supplies to your next clinic visit.

Day	Date mm/dd/yy	Morning dose hh:mm	Evening dose hh:mm	Number of Pills Taken	Comments
Day 1					
Day 2					
Day 3					
Day 4					
Day 5					
Day 6					
Day 7					
Day 8					
Day 9					
Day 10					
Day 11					
Day 12					
Day 13					
Day 14					
Day 15					

**APPENDIX A - Rucaparib Dosing Diary**  
Page 2/2

**Patient Initials:** \_\_\_\_\_  
**Treatment Cycle #:** \_\_\_\_\_

**Patient Study ID:** \_\_\_\_\_  
**Dose:** \_\_\_\_\_

- 1) Take the number of pills prescribed by your study doctor twice a day at approximately the same time each day. Take your pills with an 8oz glass of water with or without food.
- 2) If you forget to take your pills at the right time, you can take them as soon as you remember on that day as long as it's not more than 4 hours after the usual time.
- 3) If you miss taking your pills by more than 4 hours, the dose is missed. Do not take extra pills with your next dose to try and make up for the missed dose.
- 4) Complete one line of the diary each day and write the total number of pills taken in the morning and in the evening. If you've missed a dose, briefly explain why in the comments.
- 5) Please bring this diary as well as all empty containers and any unused supplies to your next clinic visit.

Day	Date mm/dd/yy	Morning dose hh:mm	Evening dose hh:mm	Number of Pills Taken	Comments
Day 16					
Day 17					
Day 18					
Day 19					
Day 20					
Day 21					
Day 22					
Day 23					
Day 24					
Day 25					
Day 26					
Day 27					
Day 28					
Day 29					
Day 30					
Day 31					

**Patient Signature** \_\_\_\_\_ **Date** \_\_\_\_\_

## APPENDIX B – PROSTATE CANCER CLINICAL TRIALS WORKING GROUP 3 (PCWG3)

The PCWG3 was created to more accurately assess bone lesions and to describe PSA based progression. PCWG3 rules were designed to be used in conjunction with radionuclide ( $^{90}\text{mTc}$ ) bone scintigraphy and therefore should be used for all bone response assessments. Only bone lesions seen on bone scans will be followed for assessment of response.

### Bone Assessments

#### Baseline Assessment

All bone lesions may be recorded as non-target lesions only and the number of lesions should be noted.

#### Response Assessment

While on treatment, follow-up scans should be assessed for progressive disease (PD), progressive disease unconfirmed (P Du), no progressive disease (Non-PD), no evidence of disease (NED), or non-evaluable (NE).

**Table 1: Bone response assessment categories**

Bone Response	Definition
PD	2 new lesions, not flare, persistent
P Du	2 new lesions, but confirmation is required by the second scan. The temporary marker of PD should be updated to PD or non-PD upon subsequent scans. If P Du is determined on the last scan, sponsor should update to PD upon analysis.
Non-PD	At least 1 bone lesion present, but not enough to trigger PD.
NE	Status of bone lesions cannot be determined.
NED	No lesions are seen on bone scan (either none at baseline or all have resolved).

#### Rules of Progressive Disease

- 2+2 Rule: If 2 new lesions appear on the first scan after the initiation of treatment, the response is classified as P Du and another scan is performed  $\geq 6$  weeks.
  - If the next scans show at least 2 new bone lesions in addition to those seen in the prior scan, the prior scan is to be considered confirmed PD.
  - If the next scan does not show at least 2 additional new bone lesions the lesions seen on the prior scan are considered pre-existing lesions. The bone response on the prior scan is updated to non-PD and new lesions seen on the first scan are ignored.
- Once outside of the flare window (the first 12 weeks of treatment) the appearance of new lesions must be confirmed with a second scan  $\geq 6$  weeks after the first scan.

- If  $\geq 2$  new lesions appear on a scan the scan will be classified as P Du until a second scan confirms lesion persistence.
  - If lesions are persistent on the second scan, the prior response will be updated to PD.
  - If the lesions disappeared on the second scan, the prior response is updated to non-PD.
- If 1 new bone lesion is seen on one scan classifying the scan as non-PD, but the following scan shows an additional new lesion (2 new lesions total between subsequent scans) the second scan will be classified as PD.
- Diffuse skeletal tumor involvement may result in a superscan. In this case, distinguishing between individual new bone lesions may be impossible. If a superscan occurs after baseline, the response will be considered PD and no further confirmation scans are required.

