8. If treatment is discontinued prior to PSA progression, PSA testing will continue throughout follow-up until PSA progression or start of another treatment. Patients who have PSA progression prior to discontinuing treatment do not need to have PSA testing performed during follow-up.
9. Rucaparib will be administered as described in Section 6.
10. Blood collection for biomarkers will be collected at screening, C3D1, C7D1, and confirmed PSA disease progression ( $\pm 7$  days), if applicable, or at EOT visit (whichever occurs first).

11. For patients enrolled with an intact prostate, urine collection for biomarkers will be collected at screening, C3D1, C7D1, and confirmed PSA disease progression ( $\pm$  7 days), if applicable, or at EOT visit (whichever occurs first).
12. Archival tissue will be collected at screening (if available). Archival tissue should not be cut until instructed by the central lab.
13. Genomic or genetic testing for 'BRCAness' will be confirmed with either blood or tissue based testing.
14. An optional fresh tissue biopsy may be obtained at PSA Progression Confirmation Visit ( $\pm$  28 days) for subjects with radiographic disease progression.
15. CT scans of the chest/abdomen and pelvis and NM bone scans will be done at the time of PSA Progression Confirmation Visit ( $\pm$  28 days) as defined in section 10.1.
16. Follow-up should occur every 90 days ( $\pm$  14 days) for 2 years following End of Treatment as per standard of care (section 9).
17. Coagulation Panel includes PT/INR, PTT.
18. The end of treatment visit should occur within +/-3 days of the decision to discontinue treatment. If this visit overlaps with a regularly scheduled visit, only the procedures listed in the calendar for the EOT visit will be performed.
19. To be performed only if the subject has completed hormone therapy. Screening testosterone may be performed within 84 days of study enrollment.
20. Only patients who have suspected PSA progression during a regular study visit will have testing to confirm PSA progression at their next regularly scheduled visit. **Before continuation of treatment after confirmed PSA progression, the patient must agree to sign the Treatment After Progression Informed Consent Form.** Patients may complete the assessments required for PSA progression in conjunction with the next regularly scheduled cycle visit or at EOT.

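### Appendix B's 2+2 bone rule has no time limit, so it overlaps the post-flare persistence rule on the trial's only scheduled post-baseline bone scan and can give the opposite result

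*Combined protocol and SAP*

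**What the plan says.** Appendix B of the combined protocol and SAP, under Rules of Progressive Disease, gives two ways to confirm new bone lesions.

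- **2+2 rule, triggered by scan order.** "If 2 new lesions appear on the first scan after the initiation of treatment", the response is provisional (PDu) and a rescan follows at six weeks or more. Two or more further lesions on the rescan make it confirmed PD. Otherwise, "If the next scan does not show at least 2 additional new bone lesions the lesions seen on the prior scan are considered pre-existing lesions". Appendix B then spells out the consequence: "The bone response on the prior scan is updated to non-PD and new lesions seen on the first scan are ignored". The bullet sets no time limit and makes no exception for lesions that are still there.
- **Persistence rule, triggered by time.** "Once outside of the flare window (the first 12 weeks of treatment) the appearance of new lesions must be confirmed with a second scan", again at six weeks or more. Two or more new lesions are PDu, and "If lesions are persistent on the second scan, the prior response will be updated to PD". If they have gone, the scan becomes non-PD. The first scan after treatment start is not excluded.

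Table 1 of the same appendix describes PD as two new lesions that persist and are not flare. It also covers the man with no rescan: "If P Du is determined on the last scan, sponsor should update to PD upon analysis".

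Section 8, note 15 fixes the scan schedule: "NM bone scans will be done at the time of PSA Progression Confirmation Visit", with a window of ±28 days, and Section 9.3 repeats this. The calendar shows no bone scan at the Day 1 visits from cycle 2 onward, at the End of Treatment visit itself, or in follow-up.

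**The concern.** One rule is keyed to the order of the scan and the other to its date. In a trial with early scheduled scans the two would separate naturally: the first scan would fall inside the flare window and later scans outside it. Here the first scheduled scan waits for suspected PSA progression, and Appendix B does not let a PSA rise in the first 12 weeks count as progression. The first scan is therefore normally outside the flare window and meets both triggers. The rules ask for different evidence on the rescan (additional lesions versus persistence), and the plan does not say which prevails.

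At stake is whether a man whose first bone lesions are still visible on rescan is recorded with radiographic progression. That choice should be settled before scans are classified, not afterwards by whichever bullet the reader applies.

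**Working it through.** The plan gives no figure to reproduce. The check has two parts: when the first scan falls, and what each rule returns for it.

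**1. Timing, in days from C1D1 = day 0**

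Inputs:
- Flare window: 12 × 7 = 84 days (Appendix B).
- Earliest countable PSA rise: day 84, the nominal C4D1 (3 cycles × 28 days; Appendix B, PSA Progression; Section 8).
- Confirmation: at the next scheduled visit, 28 ± 3 days later (Section 8, note 20), and at least 21 days after the rise (Appendix B).
- Scan window: ±28 days around the confirmation visit (Section 8, note 15).

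Scan day = 84 + gap to confirmation − days by which the scan precedes the visit.

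| Case | Calculation | Scan day | Week |
|---|---|---|---|
| Nominal, scan at visit | 84 + 28 − 0 | 112 | 16.0 |
| Minimum confirmation interval, scan at visit | 84 + 21 − 0 | 105 | 15.0 |
| Nominal, scan at early edge | 84 + 28 − 28 | 84 | 12.0 |
| Visit 3 days early, scan at early edge | 84 + 25 − 28 | 81 | 11.6 |
| Minimum confirmation interval, scan at early edge | 84 + 21 − 28 | 77 | 11.0 |

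Only the last two cases fall inside 84 days. Both stack a shortened interval on the full early window, and both would put the scan before the PSA rise that prompts it. Later PSA rises move every row later. The overlap of the two rules is therefore the planned case.

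**2. What each rule returns for a first scan after week 12 with 2 or 3 new lesions**

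| First-scan lesions on rescan | Additional new lesions on rescan | 2+2 rule | Persistence rule | Agree? |
|---|---|---|---|---|
| Persist | 0 or 1 | non-PD | PD | No |
| Persist | 2 or more | PD | PD | Yes |
| Gone | 0 or 1 | non-PD | non-PD | Yes |
| Gone | 2 or more | PD | non-PD | No |

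The first row is the main conflict, and Table 1's description of PD sides with the persistence rule. The last row is a conflict in the opposite direction about the first scan. There the additional lesions would open their own PDu on the rescan under the persistence rule, so the disagreement may end as one of date and not of status.

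**3. Reach**

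A conflict needs two or more new bone lesions on the first scan, a rescan at 42 days or later that the calendar does not schedule, and a result in the first or last row. With no rescan, Table 1 gives PD and the question does not arise. As scale only, one man in 15 is 1/15 = 6.7 percentage points. The documents give no basis for saying how many men would be affected.

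**The case against.** The best answer is that the plan already points to one reading. The persistence bullet's opening words mark a change from what precedes it, so 2+2 is naturally the rule for inside the flare window. Table 1 then confirms that persistent lesions not due to flare are PD. This is probably the intent, and on that reading the conflict disappears. It does not settle the matter, because the 2+2 bullet is written without that limit and, taken literally, reverses persistent post-flare lesions to non-PD.

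The objection does succeed against several stronger inferences a reader might draw:

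- **That Table 1 adds a third, inconsistent answer.** Its conversion of PDu to PD is a fallback for a missing later scan. For lesions that persist it agrees with the persistence rule. A man who is PD if never rescanned but non-PD if rescanned arises only when 2+2 is applied after week 12. No error in the fallback is shown.
- **That the concordance objective (1.3.2) is distorted.** Its stated endpoint compares PSA with radiographic detection of any measurable new lesion, not with Appendix B PD. Later re-scoring does not undo a detection. The link holds only if the objective is in fact scored by Appendix B PD.
- **That biopsy selection changes.** The optional biopsy is due within 28 days of the confirmation visit, and the rescan comes at least 42 days after the first scan. The rescan can fall inside the biopsy window only if the first scan preceded the visit by at least 42 − 28 = 14 days.
- **That calling lesions pre-existing contradicts the entry criteria.** Section 5.2.1 excludes metastases on conventional scans but permits disease seen on molecular imaging, and screening scans may be up to 90 days old. Disease not visible on conventional scans at entry is therefore possible.

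**Conclusion.** The concern holds as a contradiction in the written rules. For the only scheduled post-baseline bone scan, the 2+2 and persistence rules both apply literally. They disagree when two or more new lesions persist with fewer than two additional ones, and again when those lesions vanish while two or more others appear. Table 1 indicates which answer was probably meant in the first case, but the 2+2 bullet still says otherwise.

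The effect is small. It touches exploratory radiographic reporting, mainly the Section 11.3 summary of men with documented radiographic progression, and only in men who have an unscheduled rescan. A reader might infer that the efficacy conclusions are at risk, but the documents do not support that: PSA-PFS depends on PSA and death, and PSA50, OS and safety do not use the bone classification.

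The conclusion assumes that a PSA rise in the first 12 weeks does not prompt the confirmation visit, as Appendix B provides, and that day 84 counts as the end of the flare window. An unscheduled, clinically indicated scan could fall earlier, where 2+2 would apply without conflict.

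**What to change.** In Appendix B, Rules of Progressive Disease:

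1. Limit the 2+2 bullet to a first post-treatment scan taken within the first 12 weeks. Say on which side day 84 falls, because the early edge of the nominal scan window lands there.
2. State that for a first scan after week 12, the planned case here, the persistence rule governs: two or more new lesions are PDu, and become PD if they persist on rescan, consistent with Table 1.

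Leave Table 1's conversion of PDu without a rescan to PD as it stands; no separate PDu category is needed. No new dating rule is needed either, since the persistence bullet already updates the earlier scan.

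The cost is a phrase and a sentence in Appendix B. It needs no additional scans, visits, patients or analyses, and should be settled before any bone scans are classified for analysis.
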